Official Title:

The Effect of EMG Activity on Anesthetic Depth Monitoring :
Comparison Between Phase Lag Entropy and BIS

Date of the document: September 8th, 2017

NCT03230929

Study Protocol

Objectives

Phase lag entropy (PLE) is an index that quantifies the complexity of functional connections occurring between measurement areas of electroencephalogram (EEG). It records the electric activity signal of the brain via a sensor attached to the scalp, especially forehead, amplifies the measured EEG signal via the measurement module, and then processes the data. In this study, we will investigate whether the measurement method of the depth of anesthesia based on the PLE using phase lag entropy monitor (PLEM) 100 rather than the BIS algorithm reflects the anesthetic depth well without being affected by the electromyogram (EMG) activity.

Design

Prospective observational study

Inclusion criteria

Among adult males and females between the ages of 20 and 60, those who can voluntarily express their intention to participate in research, corresponding to the classification of physical status I and II of the American society of anesthesiologists (ASA).

Exclusion criteria

Patients who have lesions that can affect EEG such as cerebral hemorrhage, cerebral apoplexy and epilepsy and who have disease that can affect EMG such as muscular dystrophy, muscle stiffness, inflammatory muscular lesions, metabolic myopathy, congenital myopathy, myasthenia gravis are excluded from the subject.

Classification of physical status by ASA

Class I - healthy normal patient

Class II - patients with mild systemic disease but no functional limitation

Methods

Intravenous administration of 2% propofol and remifentanil would be done for total intravenous anesthesia. After intravenous injection of rocuronium 0.6 mg/ kg for muscle relaxation, endotracheal intubation would be performed. Then, anesthesiologist attaches the sensors of bipectral index (BIS) and PLEM 100 on the forehead of the patient, and adheres the neuromuscular monitoring device on the medial side of the wrist and the ipsilateral thumb to continuously monitor the state of consciousness and muscle relaxation before, during and after surgery. Before the end of surgery, the degree of neuromuscular relaxation should be within deep block (train-of-four count < 2) and the concentration of 2% propofol should be adjusted for maintaining BIS between 50 and 60. Reversal of muscle relaxant could be performed by intravenous injection of sugammadex 4 mg/ kg in the case of deep neuromuscular relaxation, and 2 mg / kg in the case of shallow muscle relaxation degree under neuromuscular monitoring. After then, monitor and record the values of BIS, PLEM 100, and neuromuscular monitoring in 1 minute increments for 5 minutes.

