Official Title:

The Effect of EMG Activity on Anesthetic Depth Monitoring :
Comparison Between Phase Lag Entropy and BIS

Date of the document: September 8th, 2017

NCT03230929

Statistical Analysis Plan

Paired t-test could be used for verifying the statistical difference of the bispectral index (BIS) values and phase lag entropy (PLE) before and after sugammadex administration for reversal of muscle relaxation. We will proceed with the post-hoc test for BIS values and PLE measured at every 1 minute for 5 minutes after administration of sugammadex. If the P value is less than 0.05, it is interpreted as statistical significance.

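### The study sets out to compare PLE with BIS, but no planned test asks whether BIS changed more than PLE after sugammadex.

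*Protocol*

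**What the plan says.** The title announces a "Comparison Between Phase Lag Entropy and BIS". The Objectives ask whether PLE, as opposed to BIS, "reflects the anesthetic depth well without being affected by the electromyogram (EMG) activity".

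Under Methods, the only hypnotic rule is that "the concentration of 2% propofol should be adjusted for maintaining BIS between 50 and 60", and that sentence is tied to the period before surgery ends. Remifentanil appears only in the description of the regimen: "Intravenous administration of 2% propofol and remifentanil would be done for total intravenous anesthesia". After reversal the instruction is "After then, monitor and record the values of BIS, PLEM 100, and neuromuscular monitoring in 1 minute increments for 5 minutes". No infusion rate or drug concentration is on that list, and no rule covers the infusions during those five minutes.

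The SAP has one main test: "Paired t-test could be used for verifying the statistical difference of the bispectral index (BIS) values and phase lag entropy (PLE) before and after" sugammadex. It adds a "post-hoc test for BIS values and PLE measured at every 1 minute for 5 minutes after administration of sugammadex" and a 0.05 threshold. It does not say which reading is the before value, and it does not mention comparing the change in one index with the change in the other.

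**The concern.** The research question is about a difference between two monitors, and the natural product of the SAP is two separate P values (plus their by-minute follow-ups). If BIS is significant and PLE is not, the obvious write-up is that EMG disturbs BIS and spares PLE. That conclusion needs a test of the difference in changes, and none is planned. Two indices that moved by the same amount can fall on opposite sides of 0.05 by chance.

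The design adds to this. The study is observational, with no control period or group described, so a before/after change combines returning EMG activity with any change in anaesthetic level. Simultaneous readings of both indices give some protection, because a change in depth common to both can be subtracted out, but only if an analysis does the subtraction. At stake is whether the central comparative claim has any direct statistical support.

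**Working it through.** **Plan figure to reproduce.** None. The documents state no sample size, SD, effect size or power, so everything below is illustration.

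**Inputs.** From the SAP: paired t-test, threshold 0.05. Assumed: two-sided testing (the SAP does not say), n = 30, SD of change 8 points for each index, correlation 0.5 between the two changes, no EMG effect, and a drift d of 2 to 5 points in anaesthetic level.

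**Model.** BIS change = d + e1 and PLE change = r·d + e2, where r is the PLE movement per BIS point. Simulated with 200,000 trials per case.

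**Step 1: each index alone.** SE = 8/√30 = 1.46, critical t on 29 df = 2.045. At d = 3 the noncentrality is 3/1.46 = 2.05, so the BIS test is significant in about 51% of trials although EMG does nothing.

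**Step 2: the direct contrast.** SD of (BIS change − PLE change) = √(64 + 64 − 2 × 0.5 × 64) = 8, so its SE is also 1.46. Its mean is (1 − r)·d, which is 0 at r = 1 whatever the drift.

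**Step 3: equal scales (r = 1).**

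| Drift (points) | BIS significant, PLE not | PLE significant, BIS not | Both significant | Contrast rejects (two-sided) |
|---|---|---|---|---|
| 2 | 14% | 14% | 13% | 5% |
| 3 | 17% | 17% | 34% | 5% |
| 4 | 13% | 13% | 62% | 5% |
| 5 | 6% | 6% | 85% | 5% |

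Check: adding the BIS-only and both-significant rates before rounding gives 0.136 + 0.127 = 0.263, 0.170 + 0.340 = 0.510, 0.130 + 0.624 = 0.754 and 0.061 + 0.850 = 0.911. Exact noncentral-t values for the BIS test are 0.262, 0.510, 0.754 and 0.911.

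**Step 4: sensitivity at d = 3, r = 1.** The rate of BIS significant, PLE not is 5–17% over n = 20 to 50 and SD 6 to 12. At n = 30 and SD 8 it is 20.5%, 13% and 7.5% for correlations of 0.3, 0.7 and 0.9.

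**Step 5: unequal scales, drifts 2 to 5.**

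| r | BIS significant, PLE not | Contrast rejects with BIS > PLE |
|---|---|---|
| 0.7 | 18–35% | 6–17% |
| 0.5 | 21–54% | 10–38% |
| 1.3 | 0.5–9% | under 1% |

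For example, at r = 0.7 and d = 5 the contrast mean is 0.3 × 5 = 1.5, noncentrality 1.5/1.46 = 1.03, rejection rate 17%. At r = 1.3 the errors run the other way: PLE significant and BIS not in 8–29%, and the contrast rejects in 7–17% two-sided.

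**The case against.** The best reply is that the SAP wording is loose enough to cover a BIS-versus-PLE comparison. It is loose, but the before-and-after phrasing points to one test per index, and comparing raw BIS with raw PLE values would not test change either. What stands is that this is the natural reading, not the only one.

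A second reply is that the contrast is not a cure: it subtracts raw points, the documents describe neither scale, and a significant result could reflect unequal response to depth. That stands, and the last table shows it. At r = 0.7 and 0.5 the contrast still errs less often than separate tests.

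A reader might also infer three stronger claims that the documents do not support.

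- *Separate testing is biased toward PLE.* At equal scales the two discordant patterns are equally likely, and from a drift of 3 points the commonest result is both indices significant, which would count against PLE being unaffected. A lean toward PLE arises only if PLE responds less than BIS, and the documents do not say so.
- *Depth will shift after sugammadex and be blamed on EMG.* The infusion policy in that window is unstated. Silence is missing detail; it does not show that infusions were reduced or that BIS-targeted titration continued and masked an EMG effect.
- *The before value must be an average of several readings.* Against a single last reading, a five-reading baseline changes the SE of the mean change by anything from −42% (independent minutes) to +15% (autocorrelation 0.9), so it is a trade-off. The baseline only needs defining.

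**Conclusion.** The concern holds for the missing contrast. The Protocol poses a comparative question and the SAP, as most naturally read, does not test it. That gap needs no numerical assumption. Its size does: 6–17% discordant results in each direction, against 5% two-sided for the contrast, rests on n = 30, SD 8, correlation 0.5, equal scales and a shared drift of 2 to 5 points. If PLE moves 0.5 to 0.7 points per BIS point, the contrast still falsely favours PLE in 6–38% of trials at these drifts, so its protection is partial.

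The unrecorded drug settings are secondary. They matter because, without them, nobody could later see whether drug delivery changed during the five minutes. The study can run as written, but the analysis should be amended before its comparative claim is relied on.

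**What to change.** **SAP.** Add one planned paired contrast with a 95% CI, named as the analysis that answers the comparative question: within-patient BIS change minus PLE change, each taken from the last reading before sugammadex to the mean of the five post-dose readings. State beside it that a shared change in depth cancels only to the extent that the two scales respond alike. The separate tests can stay as description of each index.

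**Record form.** Note the propofol and remifentanil settings at the pre-dose reading and at each of the five post-dose minutes, and report them descriptively. Do not adjust for them, since they may themselves respond to BIS.

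**Cost.** Two drugs at six times is 2 × 6 = 12 extra values per patient, a few SAP sentences and one more analysis. The contrast uses BIS and PLE readings that the plan already needs, and no extra patients or procedures are required.

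### EMG activity, the factor in the title and objective, is not named for recording and enters no analysis, so the planned tests show only a change after sugammadex

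*Protocol*

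**What the plan says.** The Protocol title names the factor under study: "The Effect of EMG Activity on Anesthetic Depth Monitoring". The Objectives ask whether the PLE-based measure "reflects the anesthetic depth well without being affected by the electromyogram (EMG) activity". The only other mention of EMG in the Protocol is an exclusion criterion, for patients with "disease that can affect EMG such as muscular dystrophy" and similar conditions.

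Under Methods, the BIS and PLEM 100 sensors go on the forehead and the neuromuscular device on the wrist and thumb. Before the end of surgery a deep block is asked for, and "the concentration of 2% propofol should be adjusted for maintaining BIS between 50 and 60". After reversal, staff are to "monitor and record the values of BIS, PLEM 100, and neuromuscular monitoring in 1 minute increments for 5 minutes".

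The SAP proposes a paired t-test of BIS and PLE "before and after sugammadex administration for reversal of muscle relaxation", then a post-hoc test of both at each of the five minutes, at a 0.05 level. Apart from the repeated title it does not mention EMG, and it does not use the neuromuscular values. Neither document gives a sample size, SD or expected effect.

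**The concern.** The exposure in the research question is missing from the data the plan names and from the analysis. In the SAP the sugammadex injection stands in for EMG: it is assumed that EMG is low before and higher after. Nothing in the analysis checks this, and nothing separates EMG from other things that may change in the same five minutes.

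At stake is the claim the study is set up to make. If BIS moves and PLE does not, the natural conclusion will be that PLE is resistant to EMG. The planned analysis could not support that conclusion. Two before/after tests with different verdicts do not show that the two indices differ. Even a real difference between them could come from a change in depth to which they respond unequally.

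**Working it through.** **Step 1. Where EMG appears.**

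| Place | Role of EMG |
|---|---|
| Title (both documents) | factor under study |
| Protocol, Objectives | the influence PLE should be free of |
| Protocol, Exclusion criteria | diseases that affect it are excluded |
| Protocol, Methods, recorded values | not named |
| SAP, both analyses | no term |

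**Step 2. What the before/after contrast can carry.** All patients are observed through reversal, so time, reversal and any EMG rise coincide. The wrist and thumb values can confirm that block was reversed, but they are not taken at the forehead and are not analysed. BIS and PLE are themselves depth indices and are recorded each minute, but they are the measures being tested for EMG contamination. No depth record independent of EMG, such as propofol and remifentanil delivery, is named for the five minutes. Three explanations of a change therefore remain open: EMG, reversal by another route, and lightening anesthesia.

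**Step 3. What separate tests would show (illustration).** The documents give only the 0.05 level; two-sided testing and every other input are assumed. The change in each index is drift δ plus N(0,1) noise, with correlation ρ between the monitors. Each test is t = mean/(s/√n).

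Take no EMG effect, the same δ for both indices, and ρ = 0.5. The difference in change (BIS minus PLE) has mean δ − δ = 0 and variance 1 + 1 − 2(0.5) = 1, so its test rejects in 5%. Simulation (100,000 trials per cell) gives, for BIS significant and PLE not:

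| n | δ = 0.3 | δ = 0.5 |
|---|---|---|
| 20 | 13.1% | 17.1% |
| 30 | 15.8% | 12.8% |
| 40 | 17.0% | 8.5% |

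The rate falls at larger n and δ because both tests then become significant. The 5% counts both directions, whereas the table counts one.

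**Step 4. Limits of the paired difference.** Suppose PLE responds half as strongly to depth. At ρ = 0.5 the pattern in separate tests occurs in 19.6% to 54.4% of trials, and the paired difference rejects in 9.8% to 33.8%. At ρ = 0.8, n = 40, δ = 0.5, the difference has mean 0.5 − 0.25 = 0.25 and SD √(2 − 1.6) = 0.632. The noncentrality is (0.25/0.632)√40 = 2.5, so it rejects in 68%, against 53% for the separate-tests pattern. Here the paired test is worse.

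**Step 5. Choice of scale.** Propofol is adjusted to hold BIS within a range, and PLE is not controlled in that way. The SD of BIS readings before sugammadex may therefore be too small as a yardstick. If the BIS scale is a fraction k of its SD of change (PLE at 1), the difference has mean δ/k − δ and variance 1/k² + 1 − 2ρ/k. With equal drift, ρ = 0.5, n = 40, δ = 0.5:

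- k = 0.7: mean 0.214, SD √1.612 = 1.270, noncentrality 1.07, rejection 18%.
- k = 0.5: mean 0.5, SD √3 = 1.732, noncentrality 1.83, rejection 43%.

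Over n = 20 to 40 and δ = 0.3 to 0.5 the ranges are 7% to 18% and 11% to 43%, in place of 5%.

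**The case against.** The design has controls. Patients with EMG-affecting disease are excluded, deep block is asked for first, and neuromuscular values each minute can confirm reversal. Reversal of block is a plausible way to let EMG return, and a rise in BIS with a flat PLE is not readily explained by EMG being absent. The list of recorded values is not itemised and might include a monitor's EMG reading. The SAP sentence is loose enough that a direct comparison of the indices may be intended.

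Much of this stands, and it limits the point. The documents do not show that EMG will go unrecorded, only that it is not named. The reading of the SAP as separate tests is the most natural one but not the only one. The simulated figures rest wholly on assumed inputs and concern the missing contrast rather than the missing EMG value; the textual gap does not depend on them. None of this puts EMG into an analysis or supplies a depth record independent of it.

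A reader might infer that the plan at least shows the effect of block reversal. The documents do not support that: there is no unreversed comparison and no stated control of anesthetic delivery after reversal. A reader might also infer that depth goes unrecorded after reversal. That is too strong, since both indices are recorded each minute and state of consciousness is to be monitored throughout.

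**Conclusion.** The point holds and should be fixed. EMG is the factor in the title and objective, is not named for recording, and enters no analysis. As written, the plan can show a change in BIS and PLE after sugammadex but cannot attribute it to EMG, and BIS significant with PLE not would not establish that the indices differ.

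Confidence is high for the textual gap. Its size cannot be derived from the documents. Under the assumptions of equal drift of 0.3 to 0.5 SD, no EMG effect, correlation 0.5 and 20 to 40 patients, the misleading pattern arises in about 8.5% to 17% of trials. The data would still be useful; it is the conclusion that needs support or narrower wording.

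**What to change.** 1. Check whether either attached monitor displays or stores an EMG value. If so, name it in Methods and record it just before sugammadex and at minutes 1 to 5 (1 + 5 = 6 time points). Report how many patients had a rise by a threshold set in advance. As a supporting analysis, relate BIS change and PLE change to EMG change.
2. In the SAP, base the BIS-versus-PLE comparison on a within-patient test of the difference in change, on a scale fixed and justified in advance. Do not scale by the SD of readings before sugammadex. State that the test remains confounded if the indices respond differently to depth, and can then be worse than separate tests.
3. Note the propofol and remifentanil settings actually in use at the same minutes and report them with the result, without changing management. This makes a change in delivery visible; it does not adjust for it.
4. If no EMG value is available, word the conclusion as a change in BIS and PLE after sugammadex, not as an effect of EMG or of block reversal.

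The cost is a few more recorded values at six time points and one more test, with no extra patients or procedures.

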Official Title:

The Effect of EMG Activity on Anesthetic Depth Monitoring :
Comparison Between Phase Lag Entropy and BIS

Date of the document: September 8th, 2017

NCT03230929

Statistical Analysis Plan

Paired t-test could be used for verifying the statistical difference of the bispectral index (BIS) values and phase lag entropy (PLE) before and after sugammadex administration for reversal of muscle relaxation. We will proceed with the post-hoc test for BIS values and PLE measured at every 1 minute for 5 minutes after administration of sugammadex. If the P value is less than 0.05, it is interpreted as statistical significance.

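### The title and objective compare PLE with BIS, but no test stated in the SAP estimates or tests the difference between the two monitors' changes after reversal

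*SAP*

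**What the plan says.** The title announces a "Comparison Between Phase Lag Entropy and BIS". The protocol's Objectives section asks whether PLE-based measurement "rather than the BIS algorithm reflects the anesthetic depth well without being affected by the electromyogram (EMG) activity". Both are comparative, and the second also claims that PLE is not influenced by EMG.

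The SAP is three sentences long:

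- The main analysis: "Paired t-test could be used for verifying the statistical difference of the bispectral index (BIS) values and phase lag entropy (PLE) before and after" sugammadex is given.
- The follow-on analysis: "We will proceed with the post-hoc test for BIS values and PLE measured at every 1 minute for 5 minutes after administration of sugammadex". The test is not named and no contrast is defined.
- A threshold of P<0.05.

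The data for a direct comparison are planned. The protocol's Methods section tells staff to "monitor and record the values of BIS, PLEM 100, and neuromuscular monitoring in 1 minute increments for 5 minutes", so the two monitors are read together in each patient. A reading before reversal is implied, because Methods has staff "continuously monitor the state of consciousness and muscle relaxation before, during and after surgery" and the SAP's paired test needs one. Its time is not fixed.

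**The concern.** A before/after test on each index asks whether that index moved. The title asks whether one moved more than the other. The first does not answer the second: a significant BIS change beside a non-significant PLE change is not evidence that the changes differ, and two significant changes say nothing about their difference. The SAP gives no rule for combining the two results.

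Reading the objective as two single-monitor questions does not remove the problem. The PLE question then needs evidence that any change is small enough to ignore. P≥0.05 does not supply that, and no margin is stated.

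At stake is the main conclusion. The trial could report that PLE is less affected than BIS without having estimated or tested that difference.

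**Working it through.** **What each analysis targets.** Let B be a patient's BIS change (after minus before) and P the PLE change.

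- Objective and title: mean(B) against mean(P).
- SAP main test, natural reading: mean(B)=0 and mean(P)=0, tested separately.
- SAP main test, alternative reading (BIS against PLE at each time): a comparison of levels, not of B with P.
- SAP post-hoc test: contrast not stated.

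None of these is mean(B−P).

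**Inputs.** The plan has no figure to reproduce. From the documents: paired t-tests and a 0.05 level (SAP). Assumed: two-sided tests, n=20, 30 or 40, normal change scores, correlation r between B and P of 0 to 0.7, and equal change SDs unless stated. Each setting was simulated 40,000 times.

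**1. Equal true changes of 0.3 to 0.5 SD.**

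| Result | Share of trials |
|---|---|
| BIS significant, PLE not | 6.8–24.8% |
| Direct contrast significant in the BIS direction | 2.3–2.6% |
| PLE change non-significant although real | 12.9–75.4% |

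The last row can be checked with a noncentral t distribution, noncentrality d√n. For d=0.3, n=20: 0.3×4.472=1.34, non-significant in 75%. For d=0.5, n=40: 0.5×6.325=3.16, non-significant in 13%.

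**2. Unequal true changes: 1.6 SD (BIS) and 0.8 SD (PLE).**

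| n | Both separate tests significant | Direct contrast significant (r=0 to 0.7) |
|---|---|---|
| 20 | 92.3% | 67–99% |
| 30 | 98.8–98.9% | 85–100% |
| 40 | 99.8–99.9% | 94–100% |

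A twofold difference is almost always invisible to the pair of tests.

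**3. Dependence on scale (n=30, r=0 to 0.7).** The raw-point contrast was checked with unequal change SDs.

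- Equal standardized changes of 0.5 SD, SDs 10 and 7: raw changes 5 and 3.5, a difference of 1.5 points. The contrast favours BIS being more affected in 9.5–19.9%.
- The same with SDs 10 and 5: raw changes 5 and 2.5, a difference of 2.5 points; 21.6–43.1%.
- Equal raw changes of 5 points with the same SDs: 2.4–2.6%.

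What counts as equally affected therefore depends on the scale, which must be fixed beforehand.

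**4. Precision of the contrast.** In units of one index's change SD, SD(B−P)=√(2(1−r)), and the 95% CI half-width is t(0.975, n−1)×SD(B−P)/√n.

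- n=20, r=0: 2.093×1.414/4.472=0.66 SD.
- n=40, r=0.7: 2.023×0.775/6.325=0.25 SD.

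**5. Choice of the after value.** With no true difference and between-minute correlations of 0.3 to 0.9, a paired t-test on the five-minute mean has size 4.7–5.2%. Declaring a difference if any of the five minutes is significant has size 10–21%.

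**The case against.** **The error rates belong to a rule the SAP never states.** It does not say that BIS significant with PLE non-significant will be read as superiority, and the unnamed post-hoc test might have been meant to compare monitors. This is fair. The rates show what the natural reading of two tests would do; the defect itself is that no comparison is stated.

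**The 7–25% range reflects chosen settings.** Equal changes of 0.8 SD give BIS-only significance in about 0.1–7%, and changes of 1.0 SD in about 1% or less. At n=60 with 0.5 SD it falls to 2.2%. With equal raw changes and unequal SDs, BIS-only results occur in 0–2.7% and the discordance moves to PLE-only, in roughly a quarter of trials. This also stands: the size and direction of error depend on the scenario. But where changes are large the second failure takes over, because both tests are significant.

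**The contrast is not always more sensitive.** With a BIS change of 0.5 SD, no PLE change, n=20 and r=0, its power is 32%, against 54% for the BIS-only pattern. At r=0.7 the order reverses (78% against 54%). That is a cost, but the BIS-only pattern reaches its rate without controlling false claims of a difference.

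**The objective is largely about PLE, and the contrast does not isolate EMG.** BIS could move more than PLE while PLE is still affected. Methods also says "the concentration of 2% propofol should be adjusted for maintaining BIS between 50 and 60" before the end of surgery, with no matching rule for PLE, so the baselines are not handled alike. Both points stand. They call for a margin-based judgement of PLE beside the contrast and for stated limits; they do not make the contrast unnecessary.

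**Conclusion.** The concern holds and should be fixed before analysis. It rests on the text: the title and objective are comparative, and no reading of the SAP's three sentences yields an estimate or test of the difference in change. It does not rest on any one simulated figure.

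The consequences run both ways. Small to moderate equal effects can look different, and large unequal effects can look the same. Separately, a non-significant PLE change would be weak support for PLE being unaffected. The sizes are conditional on the assumed sample sizes, correlations, normality and, for the main figures, equal change SDs. The before/after tests are not wrong; they serve part of the objective, but not the comparison in the title.

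**What to change.** Make the primary analysis one paired t-test, with estimate and 95% CI, of (after minus before BIS) minus (after minus before PLE) within patient. State in advance:

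1. The time of the reading before sugammadex.
2. One after value, for example the mean of the five one-minute readings.
3. The scale: raw points if a shared scale can be justified, otherwise an external conversion. Do not standardize by the SD before sugammadex: titrating to BIS may narrow that spread for BIS and not for PLE.

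Keep the single-index tests as supportive. Judge whether PLE is unaffected by the 95% CI of its change against a margin stated in advance, not by P≥0.05.

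Report three limits: the result depends on the chosen scale; the contrast may be imprecise; and because propofol is adjusted to BIS and not PLE before reversal, the contrast does not by itself isolate EMG.

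The cost is SAP wording and one test on readings already planned, with no added patients or devices. The real work is agreeing the scale and the PLE margin, neither of which the documents supply.
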